10.1.10. Publication Policy

- The results of this study may be published or presented at scientific meetings. If this is foreseen, the investigator agrees to submit all manuscripts or abstracts to the sponsor before submission. This allows the sponsor to protect proprietary information and to provide comments.
- The sponsor will comply with the requirements for publication of study results. In accordance with standard editorial and ethical practice, the sponsor will generally support publication of multicenter studies only in their entirety and not as individual site data. In this case, a coordinating investigator will be designated by mutual agreement.
- Authorship will be determined by mutual agreement and in line with International Committee of Medical Journal Editors authorship requirements.

10.2. Appendix 2: Clinical Laboratory Tests

The tests detailed in [Table 11](#) will be performed by the central laboratory. Local laboratory samples may still be collected as needed by the site.

Local laboratory results are required for analysis of platelets during the dosing period and be available for the investigator's review prior to dosing. A sample for central analysis is obtained in parallel

Otherwise, local laboratory results are only required in the event that the central laboratory results are not available in time for either study intervention administration and/or response evaluation. If a local sample is required, it is important that the sample for central analysis is obtained in parallel.

Protocol-specific requirements for inclusion or exclusion of participants are detailed in Section [5](#) of the protocol.

Additional tests may be performed at any time during the study as determined necessary by the investigator or required by local regulations.

Pregnancy Testing:

Refer to Section [5.1](#) Inclusion Criteria for screening pregnancy criteria. Additional serum or urine pregnancy tests may be performed, as determined necessary by the investigator or required by local regulation, to establish the absence of pregnancy at any time during the participant's participation in the study.

Table 11 Protocol-Required Laboratory Tests

Laboratory Assessments	Parameters			
Hematology	Platelet Count ¹	RBC Indices: MCV MCH	WBC count (with Differential if WBC abnormal): Neutrophils Lymphocytes Monocytes Eosinophils Basophils	
	RBC Count			
	Hemoglobin			
	Hematocrit			
Clinical Chemistry	Blood Urea Nitrogen (BUN)	Potassium	Aspartate Aminotransferase (AST)/ Serum Glutamic-Oxaloacetic Transaminase (SGOT)	Total, indirect and direct bilirubin
	Creatinine	Sodium	Alanine Aminotransferase (ALT)/ Serum Glutamic-Pyruvic Transaminase (SGPT)	Total Protein

Laboratory Assessments	Parameters			
	Glucose	Calcium	Alkaline phosphatase	Albumin
Routine Urinalysis	
 • By dipstick • Microscopic examination (if blood or protein is abnormal) 			
Pregnancy testing	
 • Highly sensitive urine or serum human chorionic gonadotropin (hCG) pregnancy test (as needed for women of childbearing potential)² 			
Other Tests	
 • Follicle-stimulating hormone and estradiol (as needed only) • Serology (HIV antibody, hepatitis C virus antibody, and hepatitis D virus antibody) • Hepatitis B serology (hepatitis B surface antigen [HBsAg], hepatitis B surface antibody [anti-HBsAg], hepatitis B e antibody [anti-HBeAg], Hepatitis B virus DNA [HBV DNA], Hepatitis B virus RNA [HBV RNA], Hepatitis B core related antigen [HBcrAg]) • Other laboratory: PT, INR, aPTT, Alpha-fetoprotein, ANCA (MPO-ANCA, PR3-ANCA), APRI/Fibrosure, Complement factors C3, C4, C5a, and Bb, hs-CRP, MCP-1, angiopoietin II, PBMC, soluble protein, PAX Gene • Urine ACR • Genetic sample • Viral Sequencing: HBV Genotype, HBV DNA, HBV RNA 
All study-required laboratory assessments will be performed by a central laboratory, with the exception:
 
 • Platelet counts for investigator decisions may be drawn at local laboratory 
 • PBMCs may be processed at the local laboratory as agreed with the Sponsor in advance. 			
Additional tests listed under safety follow-up processes	
Liver Chemistry Stopping Criteria³
 
 • Viral hepatitis serology including: 
 ○ Hepatitis A IgM antibody; ○ Cytomegalovirus IgM antibody; ○ Epstein-Barr viral capsid antigen IgM antibody (or if unavailable, obtain heterophile antibody or monospot testing); ○ Hepatitis E IgM antibody ○ Hepatitis B virus DNA load ○ Hepatitis C virus RNA load ○ Hepatitis D virus antibody • PK sample • Serum creatine phosphokinase (CPK) and lactate dehydrogenase (LDH). • Fractionated bilirubin, Anti-nuclear antibody, anti-smooth muscle antibody, Type 1 anti-liver kidney microsomal antibodies and quantitative total immunoglobulin G (IgG or gamma globulins). • Serum acetaminophen adduct high performance liquid chromatography (HPLC) assay 			

Laboratory Assessments	Parameters
	
Drug Induced Vascular Inflammation and Complement Stopping Criteria
 
 • CH50 • Factor B level • Factor H level • sC5b-9
	
Hematological Stopping Criteria
 
 • anti-platelet antibodies
	
Drug Induced Kidney Injury Stopping Criteria
 
 • 24-hour urine analysis • renal ultrasound • urine microscopy • serum urea and creatinine • platelets • urgent serum vasculitis screen [including ANCA, ANA, dsDNA, cryoglobulins] • serum protein electrophoresis (SPEP)/urine protein electrophoresis (UPEP) • complement panel (C3, C4, C5a and Bb)

NOTES:

1. Platelets will require local/central lab collection while participants are on-treatment; local lab will be optional for sites during the post-treatment period
2. Urine testing will be standard for the protocol unless serum testing is required by local regulation or IRB/IEC or if urine testing is unavailable
3. Details of liver chemistry stopping criteria and required actions and follow-up assessments after liver stopping or monitoring event are given in Section 7.1 and [Appendix 6](#). All events of ALT $\geq 3 \times$ upper limit of normal (ULN) and bilirubin $\geq 2 \times$ ULN ($>35\%$ direct bilirubin) or ALT $\geq 3 \times$ ULN and international normalized ratio (INR) >1.5 , if INR measured, which may indicate severe liver injury (possible Hy's Law), must be reported as an SAE (excluding studies of hepatic impairment or cirrhosis).

10.3. Appendix 3: AEs and SAEs: Definitions and Procedures for Recording, Evaluating, Follow-up, and Reporting

10.3.1. Definition of AE

AE Definition

An AE is any untoward medical occurrence in a clinical study participant, temporally associated with the use of a study intervention, whether or not considered related to the study intervention. 
NOTE: An AE can therefore be any unfavorable and unintended sign (including an abnormal laboratory finding), symptom, or disease (new or exacerbated) temporally associated with the use of a study intervention.

Definition of Unsolicited and Solicited AE

An unsolicited adverse event is an adverse event that was not solicited using a Participant Diary and that is communicated by a participant who has signed the informed consent. Unsolicited AEs include serious and non-serious AEs.Potential unsolicited AEs may be medically attended (i.e., symptoms or illnesses requiring a hospitalisation, or emergency room visit, or visit to/by a health care provider). The participants will be instructed to contact the site as soon as possible to report medically attended event(s), as well as any events that, though not medically attended, are of participant concern. Detailed information about reported unsolicited AEs will be collected by qualified site personnel and documented in the participant's records.Unsolicited AEs that are not medically attended nor perceived as a concern by participant will be collected during interview with the participants and by review of available medical records at the next visit.Solicited AEs are predefined local at the injection site and systemic events for which the participant is specifically questioned, and which are noted by the participant in their diary.

Events Meeting the AE Definition

Any abnormal laboratory test results (hematology, clinical chemistry, or urinalysis) or other safety assessments (e.g., ECG, radiological scans, vital signs measurements), including those that worsen from baseline, considered clinically significant in the medical and scientific judgment of the investigator (i.e., not related to progression of underlying disease).Exacerbation of a chronic or intermittent pre-existing condition including either an increase in frequency and/or intensity of the condition.

- New conditions detected or diagnosed after study intervention administration even though it may have been present before the start of the study.
- Signs, symptoms, or the clinical sequelae of a suspected intervention- intervention interaction.
- Signs, symptoms, or the clinical sequelae of a suspected overdose of either study intervention or a concomitant medication. Overdose per se will not be reported as an AE/SAE unless it is an intentional overdose taken with possible suicidal/self-harming intent. Such overdoses should be reported regardless of sequelae.
- "Lack of efficacy" or "failure of expected pharmacological action" per se will not be reported as an AE or SAE. Such instances will be captured in the efficacy assessments. However, the signs, symptoms, and/or clinical sequelae resulting from lack of efficacy will be reported as AE or SAE if they fulfill the definition of an AE or SAE.

Events NOT Meeting the AE Definition

- Any clinically significant abnormal laboratory findings or other abnormal safety assessments which are associated with the underlying disease, unless judged by the investigator to be more severe than expected for the participant's condition.
- The disease/disorder being studied or expected progression, signs, or symptoms of the disease/disorder being studied, unless more severe than expected for the participant's condition.
- Medical or surgical procedure (e.g., endoscopy, appendectomy): the condition that leads to the procedure is the AE.
- Situations in which an untoward medical occurrence did not occur (social and/or convenience admission to a hospital).
- Anticipated day-to-day fluctuations of pre-existing disease(s) or condition(s) present or detected at the start of the study that do not worsen.

10.3.2. Definition of SAE

An SAE is defined as any serious adverse event that, at any dose:

a. Results in death

b. Is life-threatening

The term 'life-threatening' in the definition of 'serious' refers to an event in which the participant was at risk of death at the time of the event. It does not refer to an event, which hypothetically might have caused death, if it were more severe.

c. Requires inpatient hospitalization or prolongation of existing hospitalization

- In general, hospitalization signifies that the participant has been admitted (usually involving at least an overnight stay) at the hospital or emergency ward

for observation and/or treatment that would not have been appropriate in the physician's office or outpatient setting. Complications that occur during hospitalization are AE. If a complication prolongs hospitalization or fulfills any other serious criteria, the event is serious. When in doubt as to whether "hospitalization" occurred or was necessary, the AE should be considered serious.
 
 • Hospitalization for elective treatment of a pre-existing condition that did not worsen from baseline is not considered an AE.

d. Results in persistent or significant disability/incapacity
 
 • The term disability means a substantial disruption of a person's ability to conduct normal life functions. • This definition is not intended to include experiences of relatively minor medical significance such as uncomplicated headache, nausea, vomiting, diarrhea, influenza, and accidental trauma (e.g. sprained ankle) which may interfere with or prevent everyday life functions but do not constitute a substantial disruption.

e. Is a congenital anomaly/birth defect

f. Is a suspected transmission of any infectious agent via an authorised medicinal product


g. Other situations:
 
 • Possible Hy's Law case: ALT\geq3xULN AND total bilirubin \geq2xULN ($>35\%$ direct bilirubin) or international normalized ratio (INR) >1.5 must be reported as SAE • Medical or scientific judgment should be exercised by the investigator in deciding whether SAE reporting is appropriate in other situations such as significant medical events that may jeopardize the participant or may require medical or surgical intervention to prevent one of the other outcomes listed in the above definition. These events should usually be considered serious. 
 ○ Examples of such events include invasive or malignant cancers, intensive treatment for allergic bronchospasm, blood dyscrasias, convulsions, or development of intervention dependency or intervention abuse.

10.3.3. Definition of Cardiovascular Events

Cardiovascular Events (CV) Definition:

Investigators will be required to fill out the specific CV event page of the CRF for the following AEs and SAEs:
 
 • Myocardial infarction/unstable angina

- Congestive heart failure
- Arrhythmias
- Valvulopathy
- Pulmonary hypertension
- Cerebrovascular events/stroke and transient ischemic attack
- Peripheral arterial thromboembolism
- Deep venous thrombosis/pulmonary embolism
- Revascularization

10.3.4. Recording and Follow-Up of AE and SAE

AE and SAE Recording

- When an AE/SAE occurs, it is the responsibility of the investigator to review all documentation (e.g. hospital progress notes, laboratory, and diagnostics reports) related to the event.
- The investigator will then record all relevant AE/SAE information in the CRF.
- It is **not** acceptable for the investigator to send photocopies of the participant's medical records to GSK in lieu of completion of the GSK required form.
- There may be instances when copies of medical records for certain cases are requested by GSK. In this case, all participant identifiers, with the exception of the participant number, will be redacted on the copies of the medical records before submission to GSK.
- The investigator will attempt to establish a diagnosis of the event based on signs, symptoms, and/or other clinical information. Whenever possible, the diagnosis (not the individual signs/symptoms) will be documented as the AE/SAE.

Assessment of Intensity

The investigator will assess the intensity for each AE and SAE reported during the study and assign it to 1 of the following categories:

- Mild: An event that is easily tolerated by the participant, causing minimal discomfort and not interfering with everyday activities.
- Moderate: An event that causes sufficient discomfort and interferes with normal everyday activities.
- Severe: An event that prevents normal everyday activities. An AE that is assessed as severe should not be confused with an SAE. Severe is a category utilized for rating the intensity of an event; and both AE and SAE can be assessed as severe.
- An event is defined as 'serious' when it meets at least 1 of the predefined outcomes as described in the definition of an SAE, NOT when it is rated as severe.

Assessment of Causality

The investigator is obligated to assess the relationship between study intervention and each occurrence of each AE/SAE.

- A "reasonable possibility" of a relationship conveys that there are facts, evidence, and/or arguments to suggest a causal relationship, rather than a relationship cannot be ruled out.
- The investigator will use clinical judgment to determine the relationship.
- Alternative causes, such as underlying disease(s), concomitant therapy, and other risk factors, as well as the temporal relationship of the event to study intervention administration will be considered and investigated.
- The investigator will also consult the Investigator's Brochure (IB) and/or Product Information, for marketed products, in his/her assessment.
- For each AE/SAE, the investigator **must** document in the medical notes that he/she has reviewed the AE/SAE and has provided an assessment of causality.
- There may be situations in which an SAE has occurred, and the investigator has minimal information to include in the initial report to GSK. However, **it is very important that the investigator always make an assessment of causality for every event before the initial transmission of the SAE data to GSK.**
- The investigator may change his/her opinion of causality in light of follow-up information and send an SAE follow-up report with the updated causality assessment.
- The causality assessment is one of the criteria used when determining regulatory reporting requirements.

Follow-up of AE and SAE

- The investigator is obligated to perform or arrange for the conduct of supplemental measurements and/or evaluations as medically indicated or as requested by GSK to elucidate the nature and/or causality of the AE or SAE as fully as possible. This may include additional laboratory tests or investigations, histopathological examinations, or consultation with other health care professionals.
- If a participant dies during participation in the study or during a recognized follow-up period, the investigator will provide GSK with a copy of any post-mortem findings including histopathology.
- New or updated information will be recorded in the originally submitted documents.
- The investigator will submit any updated SAE data to GSK within 24 hours of receipt of the information.

The DAIDS Table [DAIDS, 2017] is used for grading AEs and provided as a guidance for patient management for the consideration of the PI. The DAIDS table will be used to

grade the severity of an AE that is not specifically identified in the grading table. In addition, all deaths related to an AE are to be classified as grade 5.

The DAIDS Table is available at the following link:

<https://rsc.niaid.nih.gov/clinical-research-sites/grading-severity-adult-pediatric-adverse-events-corrected-version-two-one>

10.3.5. Reporting of SAE to GSK

SAE Reporting to GSK via Electronic Data Collection Tool

• The primary mechanism for reporting SAE to GSK will be the electronic data collection tool.• If the electronic system is unavailable, then the site will use the paper SAE data collection tool (see next section) to report the event within 24 hours.• The site will enter the SAE data into the electronic system as soon as it becomes available.• The investigator or medically-qualified sub-investigator must show evidence within the eCRF (e.g., check review box, signature, etc.) of review and verification of the relationship of each SAE to IP/study participation (causality) within 72 hours of SAE entry into the eCRF.• After the study is completed at a given site, the electronic data collection tool will be taken off-line to prevent the entry of new data or changes to existing data.• If a site receives a report of a new SAE from a study participant or receives updated data on a previously reported SAE after the electronic data collection tool has been taken off-line, then the site can report this information on a paper SAE form (see next section) or to the medical monitor by telephone.• Contacts for SAE reporting can be found in the SRM.

SAE Reporting to GSK via Paper Data Collection Tool

• Facsimile transmission of the SAE paper data collection tool is the preferred method to transmit this information to the medical monitor.• In rare circumstances and in the absence of facsimile equipment, notification by telephone is acceptable with a copy of the SAE data collection tool sent by overnight mail or courier service.• Initial notification via telephone does not replace the need for the investigator to complete and sign the SAE data collection tool within the designated reporting time frames.• Contacts for SAE reporting can be found in the study reference manual.

10.4. Appendix 4: Contraceptive and Barrier Guidance

10.4.1. Definitions:

Woman of Childbearing Potential (WOCBP)

Women in the following categories are considered WOCBP (fertile):

1. Following menarche
2. From the time of menarche until becoming post-menopausal unless permanently sterile (see below)

Notes:

- A postmenopausal state is defined as no menses for 12 months without an alternative medical cause.
 - A high follicle-stimulating hormone (FSH) level in the postmenopausal range may be used to confirm a postmenopausal state in women not using hormonal contraception or hormonal replacement therapy (HRT). However, in the absence of 12 months of amenorrhea, confirmation with more than one FSH measurement is required.
 - Females on HRT and whose menopausal status is in doubt will be required to use one of the non-estrogen hormonal highly effective contraception methods if they wish to continue their HRT during the study. Otherwise, they must discontinue HRT to allow confirmation of postmenopausal status before study enrollment.
- Permanent sterilization methods (for the purpose of this study) include:
 - Documented hysterectomy
 - Documented bilateral salpingectomy
 - Documented bilateral oophorectomy

For individuals with permanent infertility due to an alternate medical cause other than the above, (e.g., Mullerian agenesis, androgen insensitivity, gonadal dysgenesis), investigator discretion should be applied to determining study entry.

Note: Documentation can come from the site personnel's review of the participant's medical records, medical examination, or medical history interview.

If fertility is unclear (e.g., amenorrhea in adolescents or athletes) and a menstrual cycle cannot be confirmed before first dose of study intervention, additional evaluation should be considered.

10.4.2. Contraception Guidance:

CONTRACEPTIVES ^a ALLOWED DURING THE STUDY INCLUDE:	
Highly Effective Methods^b That Have Low User Dependency Failure rate of <1% per year when used consistently and correctly.	
Implantable progestogen-only hormone contraception associated with inhibition of ovulation ^b	
Intrauterine device (IUD)	
Intrauterine hormone-releasing system (IUS) ^b	
Bilateral tubal occlusion	
Vasectomized partner Note: Vasectomized partner is a highly effective contraceptive method provided that the partner is the sole sexual partner of the woman of childbearing potential and the absence of sperm has been confirmed. If not, an additional highly effective method of contraception should be used. Spermatogenesis cycle is approximately 90 days.	
Highly Effective Methods^b That Are User Dependent Failure rate of <1% per year when used consistently and correctly.	
Combined (estrogen- and progestogen-containing) hormonal contraception associated with inhibition of ovulation ^c	
oral	
intravaginal	
transdermal	
injectable	
Progestogen-only hormone contraception associated with inhibition of ovulation ^c	
oral	
injectable	
Sexual abstinence Note: Sexual abstinence is considered a highly effective method only if defined as refraining from heterosexual intercourse during the entire period of risk associated with the study intervention. The reliability of sexual abstinence needs to be evaluated in relation to the duration of the study and the preferred and usual lifestyle of the participant.	
ACCEPTABLE METHODS ^d	
Progestogen-only oral hormonal contraception where inhibition of ovulation is not the primary mode of action	
Male or female condom with or without spermicide ^e	
Cervical cap, diaphragm, or sponge with spermicide	
A combination of male condom with either cervical cap, diaphragm, or sponge with spermicide (double-barrier methods) ^c	
a. Contraceptive use by men or women should be consistent with local regulations regarding the use of contraceptive methods for those participating in clinical studies.	

- b. Failure rate of <1% per year when used consistently and correctly. Typical use failure rates differ from those when used consistently and correctly.
- c. If locally required, in accordance with Clinical Trial Facilitation Group (CTFG) guidelines, acceptable contraceptive methods are limited to those which inhibit ovulation as the primary mode of action.
- d. Considered effective, but not highly effective - failure rate of $\geq 1\%$ per year. Periodic abstinence (calendar, sympto-thermal, post-ovulation methods), withdrawal (coitus interruptus), spermicides only, and lactational amenorrhoea method (LAM) are not acceptable methods of contraception.
- e. Male condom and female condom should not be used together (due to risk of failure with friction).

10.4.3. Collection of Pregnancy Information:

Female Participants who become pregnant

Investigator will collect pregnancy information on any female participant, who becomes pregnant while participating in this study.

The initial information will be recorded on the appropriate form and submitted to GSK within 24 hours of learning of a participant's pregnancy.

Participant will be followed to determine the outcome of the pregnancy. The investigator will collect follow up information on participant and neonate, which will be forwarded to GSK. Generally, follow-up will not be required for longer than 6 to 8 weeks beyond the estimated delivery date.

Any termination of pregnancy will be reported, regardless of fetal status (presence or absence of anomalies) or indication for procedure.

While pregnancy itself is not considered to be an AE or SAE, any pregnancy complication or elective termination of a pregnancy for medical reasons will be reported as an AE or SAE.

A spontaneous abortion (occurring at <22 weeks gestational age) or still birth (occurring at >22 weeks gestational age) is always considered to be an SAE and will be reported as such.

Any SAE occurring as a result of a post-study pregnancy which is considered reasonably related to the study intervention by the investigator, will be reported to GSK as described in [Appendix 3](#). While the investigator is not obligated to actively seek this information in former study participants, he or she may learn of an SAE through spontaneous reporting.

Any female participant who becomes pregnant while participating will discontinue study intervention or be withdrawn from the study

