5.1. Inclusion Criteria

AGE	
 At least 18 years of age at the time of signing the informed consent. [if country/site age requirements for consent differ, the more stringent (e.g., higher age) restriction will be required for that country/site].
TYPE OF PARTICIPANT AND DISEASE CHARACTERISTICS	
 Participants who have documented chronic HBV infection \geq6 months prior to screening AND currently receiving stable nucleos(t)ide analogue therapy, defined as no changes to their nucleos(t)ide regimen from at least 6 months prior to screening and with no planned changes to the stable regimen over the duration of the study Plasma or serum HBsAg concentration >100 IU/mL Plasma or serum HBV DNA concentration must be adequately suppressed, defined as plasma or serum HBV DNA <90 IU/mL HBeAg-negative Alanine Transaminase (ALT) $\leq 2 \times$ ULN
SEX	
 Male and/or Female 
 A male participant is eligible to participate if they agree to the following during the intervention period and for at least 90 days after the last dose of study treatment 
 Refrain from donating sperm AND be abstinent from heterosexual intercourse as their preferred and usual lifestyle (abstinent on a long term and persistent basis) and agree to remain abstinent OR Must agree to use contraception/barrier as detailed below 
 Agree to use a male condom [and should also be advised of the benefit for a female partner to use a highly effective method of contraception as a condom may break or leak] when having sexual intercourse with a woman of childbearing potential who is not currently pregnant A female participant is eligible to participate: 
 If she is not pregnant or breastfeeding AND at least one of the following conditions applies: 
 Is not a woman of childbearing potential (WOCBP) OR is a WOCBP and using a contraceptive method that is highly effective (with a failure rate of $<1\%$ per year), preferably with low user dependency during the intervention period and for at least 90 days after the last dose of study treatment

iii. A WOCBP must have both

1. A confirmed menstrual period prior to the first dose of study intervention [additional evaluation (e.g., amenorrhea in athletes, birth control) should also be considered]

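### Appendix 4 lists as acceptable some contraceptive methods for women that fail Inclusion criterion 7, and no text says how the two passages fit together

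*Protocol*

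**What the plan says.** Protocol Section 5.1, under the sex criterion (Inclusion 7), accepts a female participant who is not of childbearing potential or who "is a WOCBP and using a contraceptive method that is highly effective". The criterion defines highly effective as a failure rate below 1% per year and sets the period: "preferably with low user dependency during the intervention period and for at least 90 days after the last dose of study treatment". For male participants who are not abstinent, the same criterion has a different rule: "Agree to use a male condom" with a partner of childbearing potential. A highly effective method for that partner is only advised.

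Protocol Section 10.4.2 (Appendix 4) has a table whose heading names contraceptives "ALLOWED DURING THE STUDY INCLUDE". Two blocks of highly effective methods come first, one with low user dependency and one user dependent. A third block follows, titled "ACCEPTABLE METHODS". It contains:

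- a progestogen-only pill that does not act mainly by inhibiting ovulation;
- male or female condom;
- "Cervical cap, diaphragm, or sponge with spermicide";
- double-barrier combinations.

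Footnote d describes this block as "Considered effective, but not highly effective" and gives a failure rate of 1% per year or more.

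Section 5 bars waivers of enrolment criteria, and Section 8 repeats that waivers are not allowed.

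**The concern.** The two sections classify the same methods differently. Section 5.1 gives a threshold for women but no list of qualifying methods; the only list in the protocol is in Appendix 4. Someone at a site checking a named method, either at entry or when a participant changes method during the study, could reasonably turn to that list and find the method described as acceptable.

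If that happened at entry, a woman could be enrolled on a method that fails the inclusion criterion. Because waivers are barred, that would be an eligibility deviation that nobody could have approved in advance. If it happened later, she could be told that her new method is permitted when the criterion says otherwise. In both cases the consequence concerns participant safety and site conduct: a possible pregnancy exposed to an investigational product. Section 10.4.3 requires a participant who becomes pregnant to stop study intervention or be withdrawn.

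**Working it through.** No arithmetic on power, precision or event counts applies. The check sets the two passages side by side and tests whether other text reconciles them.

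**Step 1: the thresholds.**

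| Source | Who or what | Failure rate per year |
|---|---|---|
| Section 5.1, Inclusion 7 | Method required of a woman of childbearing potential | below 1% |
| Section 10.4.2, first two blocks | Highly effective methods | below 1% |
| Section 10.4.2, third block, footnote d | Acceptable methods | 1% or more |

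Below 1% and 1% or more are mutually exclusive. By the protocol's own definitions, every method in the third block fails the inclusion threshold when used alone.

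**Step 2: the period covered.** The inclusion rule runs to at least 90 days after the last dose. With the last planned dose on Day 78, that is Day 78 + 90 = Day 168, between the Week 24 (Day 162) and Week 28 (Day 190) visits. The rule therefore governs continued participation well into follow-up as well as entry.

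**Step 3: could the third block be meant for men?** The male condom entry could be, since Section 5.1 asks non-abstinent male participants to use one. That cannot explain the progestogen-only pill, the female condom, or the cap, diaphragm or sponge as methods a female participant might use. No text restricts the block to male participants, to their partners, or to use on top of a highly effective method.

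**Step 4: do the local-regulation clauses settle it?** Section 5.1 and footnote a both ask that contraceptive use follow local regulations. Neither says which of the two protocol standards applies. Footnote c narrows the acceptable methods only where local rules require it, so it does not remove the block elsewhere.

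**Step 5: is footnote d only a warning label?** The same footnote names methods that are not acceptable: periodic abstinence, withdrawal, spermicide alone and lactational amenorrhoea. The appendix therefore draws its own line between acceptable and not acceptable, and places the methods with failure rates of 1% or more on the acceptable side.

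**Step 6: worked case.** A woman of childbearing potential relies only on a diaphragm with spermicide. Under Section 5.1 she does not meet the criterion. Under Section 10.4.2 her method is listed as acceptable. Nothing in either section tells the site how to resolve this.

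**The case against.** The strongest reply is that the controlling rule is already clear. Section 5.1 states the method standard, the failure rate and the duration in full. It refers to Appendix 4 only for further pregnancy-testing requirements, not for the choice of method. Section 8 requires sites to confirm every eligibility criterion. Appendix 4 is titled as guidance, sorts methods into tiers, and openly labels the third tier as falling short of highly effective. A careful site reading both would apply the stricter text. There are also safeguards: Section 5.1 requires a negative pregnancy test within 24 hours before the first dose, and the Schedule of Activities repeats testing during treatment and follow-up.

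Most of this stands, and it limits the point. It does not remove it, because a reader still finds methods labelled acceptable that the criterion excludes, with no linking sentence.

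The table layout was lost when the text was read from PDF, so the third block may be a parallel section and not a sub-list of allowed contraceptives. Its title would still call those methods acceptable.

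Three stronger readings are tempting and are not supported:

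- *That Appendix 4 is the sites' working reference for contraception.* No text says so.
- *That every enrolled woman of childbearing potential is affected.* Only one relying solely on a third-block method would be.
- *That every entry in the block conflicts with Section 5.1.* The male condom entry has a proper use for male participants.

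**Conclusion.** The inconsistency is real and narrow. For women of childbearing potential, Section 5.1 and Section 10.4.2 cannot both be followed as written for the progestogen-only pill described, the female condom, the cap, diaphragm or sponge, or the double-barrier combinations when used alone.

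The risk is confined to women relying solely on one of these methods, at sites that consult Appendix 4 for permitted methods. The documents do not say how many women of childbearing potential are expected; the whole study targets about 20 participants and is capped at 24. The conclusion assumes only that some sites may look to the protocol's one list of methods when a named method is in question.

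This is a wording inconsistency that bears on participant safety and eligibility. It does not touch the sample size, the primary endpoint, the estimands or the analysis. Which standard is clinically right is not a question this review answers.

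**What to change.** In the next amendment, reconcile Section 5.1 with Section 10.4.2. Either make both state the same standard for women of childbearing potential, or add a sentence to the third block of the Appendix 4 table saying whom it serves and how it relates to Inclusion criterion 7. The choice of clinical standard is the sponsor's. The cost is one text edit, with no change to the SAP.
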